3.3.3 Exit criteria

Participants may withdraw from the study under any circumstances and should withdraw from the study in the following situations:

- (1) The patient developed life-threatening complications;
- (2) The occurrence of intolerable clinical symptoms related to the therapeutic drug;
- (3) Pregnancy was combined during the study;
- (4) The subject was assessed by the investigator as needing to withdraw from the trial;
- (5) Unwilling to continue to participate in the study/informed consent withdrawal;
- (6) Disappearance.

If the subject wishes to discontinue participation in the study, he/she will participate in the termination visit to complete the test items of the termination visit.

4. Research plan

4.1 Research phase and process

This study plans to enroll 140 patients with maintenance peritoneal dialysis who meet the inclusion and exclusion criteria, and is expected to be conducted in 5 centers. The study period for each subject is 6 months, and the entire study project will be completed in about 1 year. The study was divided into two phases: screening and treatment.

Screening period: Within 1 month before enrollment, patients who meet the inclusion criteria are initially screened, including physical examination, blood pressure

measurement, body weight measurement, BMI calculation, CI calculation, skinfold thickness measurement, waist circumference and grip strength measurement, upper arm muscle circumference measurement, SGA score, urine volume, ultrafiltration volume, biochemical and liver and kidney function tests, serum albumin, prealbumin, nPCR, nPNA, Kt/V and Ccr, Nt-pro BNP, hepatitis B related antigen and antibody, hepatitis C antibodies, HIV antibodies and other indicators were measured, and subjective nutritional score (SGA) and PET tests were performed. At the same time, explain the purpose, method, benefits and risks of this study to the patient and obtain his/her written informed consent. At the same time, inform the patient

The patient introduces the specific protocol and precautions of this study.

Treatment Phase: The treatment phase begins after enrollment. Each participant receives a regimen of 1 bag of amino acid peritoneal dialysis and 2-4 bags of glucose peritoneal dialysis fluid daily for 6 months (the amount of glucose peritoneal dialysis fluid is determined based on the treatment plan at the time of screening when the patient enters the study). The amino acid peritoneal dialysis fluid is provided by the research center, with the following composition: amino acids (15). The glucose peritoneal dialysis fluid is also provided by the research center, with the following composition: this product is a compound preparation, each 1L the composition of the solution is 1000mL, alanine 0.951g, arginine 1.071g, glycine 0.510g, histidine 0.714g, leucine 0.850g, lysine 1.020g, 1-lysine hydrochloride 0.955g, methionine 0.850g, phenylalanine 0.570g, proline 0.595g, serine 0.510g, threonine 0.646g, tryptophan 0.270g, tyrosine 0.300g, ammonia 1.393g, sodium chloride 5.380g, Calcium chloride ($\text{CaCl}_2 \cdot 2\text{H}_2\text{O}$) 0.184g, Magnesium chloride (Mg, CL2·6H2O]0.051g), Sodium lactate 4.480g, Ion concentration (mmol/L): Amino acids 87.16mmol/L, Sodium 132mmol/L, Calcium 1.25mmol/L, Magnesium 0.25mmol/L, Chlorine 105mmol/L, Lactate root 40mmol/L. The excipients of this product include hydrochloric acid and water for injection. This product is a glucose-free peritoneal dialysis solution, used as part of the peritoneal dialysis regimen

One part is used for the treatment of chronic kidney patients, especially suitable for peritoneal dialysis patients with serum albumin less than 35g/L.

The composition of glucose peritoneal dialysis fluid is shown in Figure 2:

Drug name	composition					ion concentration					osmotic pressure	pH	capacity
	C6H12O6·H2O	NaCl	C3H5NaO3	CaCl2·2H2O	MgCl·6H2O	Na	Ca	Mg	chloride	lactate			
Low Calcium Peritoneal Dialysis Solution(lactate-G1.5%)	1.5g	0.538 g	0.448g	0.0183g	0.0051g	132.01	1.25	0.25	95.04	39.97	344	4.5-6.5	2000
Low Calcium Peritoneal Dialysis Solution(lactate-G1.5%)	2.5g	0.538 g	0.448g	0.0183g	0.0051g	132.01	1.25	0.25	95.04	39.97	395	4.5-6.5	2000
Low Calcium Peritoneal Dialysis Solution(lactate-G4.25%)	4.25	0.538 g	0.448g	0.0183g	0.0051g	132.01	1.25	0.25	95.04	39.97	483	4.5-6.5	2000

Figure 2. Composition of glucose peritoneal dialysis fluid

The daily use of 1 bag of amino acid peritoneal dialysis fluid is during the nighttime sleep period, while the daily use of 2-4 bags of glucose peritoneal dialysis fluid is during the daytime. The total daily infusion volume, each infusion volume, dwell time, and each excretion volume for each subject are adjusted by the researcher based on individual patient conditions and standardized prescriptions. During treatment, subjects should follow the researcher's guidance for daily life and dietary management, and regularly visit the research center for follow-up and examinations. In the third and sixth months of treatment, subjects should repeat the screening period

All evaluation items and any adverse events or serious adverse events are recorded.

The research process is shown in Table 1:

Table 1: Research process table

Evaluate projects	Screening period/baseline	stage of therapy					
		1 month	2 months	3 months	4 months	5 months	6 months
informed consent	√	×	×	×	×	×	×
Inclusion and exclusion criteria	√	×	×	×	×	×	×
Collect demographic data	√	×	×	×	×	×	×
Symptoms (loss of appetite, nausea, vomiting, abdominal distension, Infusion pain, edema, etc.)	√	√	√	√	√	√	√

Previous illness/treatment	✓	✗	✗	✗	✗	✗	✗
Combination therapy with concomitant medication	✓	✓	✓	✓	✓	✓	✓
allergic history	✓	✗	✗	✗	✗	✗	✗
SGA	✓	✓	✓	✓	✓	✓	✓
check-up	✓	✓	✓	✓	✓	✓	✓
vital sign	✓	✓	✓	✓	✓	✓	✓
Ultrafiltration volume	✓	✓	✓	✓	✓	✓	✓
UPD	✓	✓	✓	✓	✓	✓	✓
BMI	✓	✓	✓	✓	✓	✓	✓
CI	✓	✗	✗	✓	✗	✗	✓
skin-fold thickness	✓	✗	✗	✓	✗	✗	✓
Waist circumference and grip strength, upper arm muscle circumference	✓	✗	✗	✓	✗	✗	✓
Hepatitis B related antigen antibody, hepatitis C antibody, HIV antibody	✓	✗	✗	✗	✗	✗	✗
Biochemistry and liver and kidney function (including serum albumin, Prealbumin), glycosylated hemoglobin	✓	✗	✗	✓	✗	✗	✓
White, fasting blood sugar							
Nt-Pro BNP	✓	✗	✗	✓	✗	✗	✓
nPCR	✓	✗	✗	✓	✗	✗	✓

nPNA	✓	✗	✗	✓	✗	✗	✓
Kt/V and Ccr	✓	✗	✗	✓	✗	✗	✓
PET	✓	✗	✗	✓	✗	✗	✓
adverse event	✓	✓	✓	✓	✓	✓	✓

(1) Informed Consent: Before participants join this study, their written consent, either from the participant themselves or their legal representative, must be obtained. The informed consent form should include information on the purpose, design, process, risks, benefits, rights, and obligations of the study, as well as the participant's personal information and contact details. The informed consent form should be signed jointly by the researcher and the participant or their legal representative. It's kept in the research files.

(2) Collect demographic data: After the subject is selected for this study, basic information should be recorded, including name, gender,

Age, height, weight, BMI, etc. The formula for calculating BMI is: $BMI = \frac{\text{weight (kg)}}{\text{height m}^2}$.

(3) Collect symptoms (loss of appetite, nausea, vomiting, abdominal distension, infusion pain, edema, etc.): After the subject is enrolled in this study, detailed questions should be asked about gastrointestinal related symptoms and edema, which should be recorded in CRF, and attention should be paid to whether there are causes related to this study or influencing factors.

(4) Collecting Past Medical History and Comorbidities: After a participant is enrolled in this study, their past medical history and comorbidities should be thoroughly inquired about. This includes all relevant internal and external medical conditions and surgical histories, as well as any medications currently being used or planned for use, and other treatments. The past medical history and comorbidities should be documented in the CRF, with attention to any factors relevant to this study

Or influencing factors.

(5) Inquiry of allergy history: After the subject is selected for this study, his/her allergy history should be inquired in detail, including allergen, allergic reaction and so on treatment methods, etc. Allergy history should be recorded in the CRF, and pay attention to whether there are factors or influencing factors related to this study.

(6) The improved SGA evaluation method was used. The higher the score, the worse the nutrition. Normal nutrition: 7 points; mild to moderate nutrition: 8-15 points; severe malnutrition: ≥ 16 points.

(7) Physical Examination: After the subject is enrolled in this study, a comprehensive physical examination should be conducted, including the head and face, skin system, lymph nodes, eyes, ears, nose, throat, mouth, respiratory system, cardiovascular system, abdomen, genitourinary system, musculoskeletal system, and nervous system. The results of the physical examination should be recorded in the CRF, with attention to any abnormalities or related issues clinical manifestation.

(8) Monitor vital signs: After the subject is enrolled in this study, their vital signs should be monitored regularly, including blood pressure (systolic and diastolic), heart rate (beats per minute), respiratory rate (breaths per minute), and body temperature ($^{\circ}\text{C}$). Vital signs should be measured in a resting state using the same equipment and methods. The results of the vital signs should be recorded in the CRF, noting any abnormalities abnormal or abnormal related clinical manifestations.

(9) Record urine output and ultrafiltration: After the subject is enrolled in this study, their urine output and ultrafiltration should be regularly recorded to assess renal function and peritoneal function. Urine output is the average of the 24-hour urine collected at home, and the measurement of ultrafiltration at home should be taken before and after each session of peritoneal dialysis, using the same equipment and method. The results of urine output and ultrafiltration should be recorded and evaluated. The average value for the first 1 month is in the CRF and note any abnormal or abnormal related clinical manifestations.

(10) Measure skinfold thickness: After participants are enrolled in this study, their triceps skinfold thickness should be measured regularly to assess their nutritional and physical status. The measurement of skinfold thickness should be performed on the right upper arm at the triceps area using a standard skinfold caliper. The results of the skinfold thickness should be recorded in the CRF, noting any abnormalities or related clinical manifestations.

(11) Measure waist circumference, grip strength, upper arm girth, and CI: After participants are enrolled in this study, their waist circumference, grip strength, and upper arm girth should be measured regularly

Arm muscle circumference and CI to assess their nutritional and physical status. The waist circumference measurement should be taken at the level of the lower edge of the diaphragm,

And use a soft ruler. Grip strength measurement should be taken between the thumb and index finger of the right hand, using a standard grip strength gauge. The formula for calculating CI is: $CI = \text{waist circumference (m)} / \{0.109 \times [\text{body weight (kg)} / \text{height (m)}^{1/2}]\}$. Waist circumference, grip strength, upper arm muscle

The results of the peritoneal and CI should be recorded in the CRF, noting any abnormalities or abnormal related clinical manifestations.

(12) Biochemical blood tests: After the subjects are enrolled in this study, regular biochemical blood tests should be performed, including ALT (alanine transaminase), AST (aspartate transaminase), total bilirubin, direct bilirubin, blood urea nitrogen or urea, total protein, albumin, creatinine, blood glucose, lactate dehydrogenase, K^+ , Na^+ , Ca^{2+} , Cl^- , etc., to evaluate their liver function, kidney function and metabolism

Level. The results of biochemical blood tests should be recorded in the CRF and note any abnormalities or abnormal related clinical manifestations.

(13) Detection of Nt-pro BNP: After the subjects were enrolled in this study, screening period and treatment at 3 months and 6 months Nt-The results of the pro BNP should be recorded in the CRF, noting any abnormalities or abnormal related clinical manifestations.

(14) Detection of nPCR and nPNA: After the subject is enrolled in this study, his/her nPCR and nPNA should be regularly tested to evaluate his/her protein catabolism rate and total protein nitrogen presentation rate. The results of nPCR and nPNA should be recorded in the CRF and noted whether there are any abnormal or abnormal related clinical manifestations.

(15) Calculate Kt/V and Ccr: After the subject is enrolled in this study, Kt/V and Ccr should be calculated regularly to evaluate his/her dialysis efficiency and residual renal function. The results of Kt/V and Ccr should be recorded in the CRF, and attention should be paid to any abnormalities or abnormal related conditions clinical manifestations.

(16) Conduct PET testing: After subjects are enrolled in this study, regular PET tests should be conducted to evaluate their peritoneal dialysis material transport characteristics. The PET testing method follows the standard PET (Standard PET) proposed by Twardowski. Measure the glucose concentration in the effluent and compare it with that in the infused fluid to calculate the D/P ratio and the D/D0 ratio. Based on the D/P ratio and the D/D0 ratio, subjects are categorized into four types: high transport, high average transport, low average transport, and low transport. The results of the PET testing should be

recorded in the CRF, noting any abnormalities or differences common associated clinical manifestations.

(17) Adverse events: The recording time is from the start of treatment to the end of survival follow-up, and only AE related to this study is collected, Including adverse events of special concern.

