3.2.2 Secondary endpoints

The secondary endpoint of this study was other relevant indicators of the subjects at 3 months and 6 months after treatment

The body is as follows: Mass (kg): The change in mass of the subject compared to baseline at 3 months and 6 months (Δ Body mass); BMI (kg/m^2): (Δ of the change in BMI of the subject compared to baseline at 3 months and 6 months BMI); CI: CI change value of the subject at 3 months and 6 months compared with baseline (Δ CI);

- Waist circumference and grip strength (cm/kg): The changes in waist circumference and grip strength compared with baseline at 3 months and 6 months were measured by a tape measure to measure the circumference of the narrowest part of the subject. The maximum grip strength of the subjects was measured with a grip strength gauge;
- Arm muscle circumference (cm): The change in arm muscle circumference (Δ arm muscle circumference) of the subjects compared with baseline at 3 months and 6 months was measured by a tape measure at the midpoint of the subject's upper arm and according to the formula

The calculated upper arm muscle circumference = arm circumference (cm) $0.3142 \times$ triceps skinfold thickness (mm);

Δ nPCR (g/kg/d): nPCR change values of subjects at 3 months and 6 months compared to baseline (Δ nPCR);

$\Delta nPNA$ (g/kg/d): Changes in nPNA compared to baseline at 3 months and 6 months
Value ($\Delta nPNA$).

3) Metabolic status-Glycated hemoglobin (%): Glycated hemoglobin of the subjects at 3 months and 6 months compared to baseline. White change value (Δ glycosylated hemoglobin) was measured by an automatic biochemical analyzer to measure the glycosylated hemoglobin of the subjects. Hemoglobin levels.

4) Fasting blood glucose (mmol/L): Fasting blood glucose of the subjects at 3 months and 6 months compared with baseline

Change value (Δ fasting blood glucose) was measured by an automatic biochemical analyzer to measure the subject's fasting blood glucose level.

5) Indicators of residual renal function and dialysis adequacy

- Urine volume: the change in urine volume compared with baseline at 3 months and 6 months (Δ urine volume);

- Ultrafiltration: change in urine volume compared to baseline at 3 months and 6 months (Δ ultrafiltrationmeasure);

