4.2 Data collection

4.2.1 Screening period

During the screening period, the following observations were performed on patients who met the inclusion criteria:

Informed consent: Explain the purpose, method, benefits and risks of this study to the patient, and obtain his/her written informed consent.

Inclusion/exclusion criteria: Check whether the patient meets the inclusion and exclusion criteria.

Past history/comorbidities/treatment: Record the patient's past history, comorbidities and treatment.

Comprehensive Subjective Nutritional Assessment (SGA): Using the improved method of SGA assessment in the 2010 version of The Standard Operating Procedures for Peritoneal Dialysis, patients were comprehensively assessed for nutritional status, including weight change, appetite change, gastrointestinal symptoms, activity ability and complications, physical examination, etc., and patients were divided according to the scoring results. There are three categories: normal nutrition (A), mild malnutrition (B) or severe malnutrition (C).Physical examination: Measure the patient's height, weight, blood pressure, heart rate, respiratory rate and other indicators, and calculate

BMI (BMI= body mass / height² (kg/m²)).

Blood pressure measurement: Use standardized methods and equipment to measure the patient's systolic and diastolic blood pressure and record itaverage value.

Body weight measurement: Use an electronic scale to measure the dry weight of the patient and record the value.

BMI Calculation: Calculate the patient's BMI based on weight and height data, and record its value.

CI calculation: Use the tape measure to measure the patient's waist circumference, and calculate the patient's CI value ($CI = \text{waist circumference (m)} / \{0.109 \times [\text{body weight (kg)} / \text{height (m)}]^{1/2}\}$) according to the weight and height data, and record it numeric value.

Waist circumference and grip strength measurement: Use a tape measure to measure the patient's waist circumference and record its value. Use a grip strength gauge, according to the standard method, the grip strength of each patient's left and right hands was measured once and the average value was recorded.

Triceps skinfold thickness measurement: Use a skinfold thickness gauge and follow a standardized method on the right side of the patient the triceps, the thickness of the skin fold was measured and recorded.

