4.2.2 During treatment

During the treatment period, each participant received a regimen of 1 bag of amino acid peritoneal dialysis and 2-4 bags of glucose peritoneal dialysis fluid daily for 6 months (the amount of glucose peritoneal dialysis fluid was determined based on the treatment plan at the time of screening when the patient entered the study). In the third and sixth months of the treatment period, participants should repeat all assessments from the screening phase and record any adverse events or serious adverse events. Monthly follow-up evaluations were conducted during the treatment period. Observe (infusion pain, abdominal distension), blood pressure, weight, urine volume, ultrafiltration.

5. Treatment plan

The treatment protocol of this study is as follows:

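### Waist circumference has two conflicting measuring sites, and the conicity index built on it is printed with two formulas that need checking and reconciling

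*Combined protocol and SAP*

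**What the plan says.** Section 3.2.2 makes the changes in waist circumference and in CI at months 3 and 6 secondary endpoints. For CI the entry reads "CI change value of the subject at 3 months and 6 months compared with baseline". Waist is the numerator of CI.

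**Waist site.** Three places describe the measurement:
- Section 3.2.2: "measured by a tape measure to measure the circumference of the narrowest part of the subject".
- Section 4.1, item 11: "The waist circumference measurement should be taken at the level of the lower edge of the diaphragm".
- Section 4.2.1, with no level named: "Use a tape measure to measure the patient's waist circumference and record its value".

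**CI formula.** Two places print it:
- Section 4.1, item 11, after "The formula for calculating CI is": waist / {0.109 × [weight / height^(1/2)]}. The root is on height only.
- Section 4.2.1, under "CI calculation: Use the tape measure to measure the patient's waist circumference, and calculate the patient's CI value": waist / {0.109 × [weight / height]^(1/2)}. The root is on the ratio.

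**Timing and analysis.** Table 1 schedules waist and CI at screening, month 3 and month 6. Section 4.2.2 says that at the two later visits "participants should repeat all assessments from the screening phase", and Section 4.1 says the same just before Table 1. Section 7.6.3 tests change from baseline by a paired t-test or Wilcoxon signed-rank test. Section 3.1 states that there is no control group. Nothing in the document says which site or which formula takes precedence.

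**The concern.** A paired comparison takes the same quantity to have been measured the same way at each visit. Two written landmarks leave staff in five expected centres free to follow either one. A change of landmark between a patient's baseline and a later visit would then be read as a change in the patient. In a controlled trial such a shift might fall on both arms and largely cancel; here it goes straight into the estimate. It would affect two secondary endpoints, because CI inherits any error in waist.

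The two printed CI equations are a different kind of problem. They are not rescalings of one another, because they depend on weight differently. A change in CI computed by one need not agree with a change computed by the other, even in sign.

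**Working it through.** The plan gives no CI value, no expected change in CI and no waist data, so there is no figure of its own to reproduce. All body measurements below are assumptions.

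**1. Effect of the waist site.** Both formulas are proportional to waist, so at a given weight and height a proportional shift in waist gives the same proportional shift in CI.
- Assumed waist 85 cm; assumed difference between sites 2 to 5 cm.
- 2/85 = 2.4%; 5/85 = 5.9%.
- For scale, a 3% weight gain at constant waist moves the Section 4.2.1 CI by 1/√1.03 − 1 = −1.5%.

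Between visits, the shift enters the change directly. If one of five equally sized centres switched site after baseline, the mean change in waist over all patients would move by 1/5 × 2 = 0.4 cm to 1/5 × 5 = 1.0 cm. Between centres that each keep to one site, a constant offset largely cancels within patients. It then mainly distorts pooled levels and spread.

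**2. Size of the formula difference.** Let C be waist (m), W weight (kg) and H height (m).
- A (Section 4.1, item 11) = C / (0.109 × W / √H)
- B (Section 4.2.1) = C / (0.109 × √(W/H))
- B/A = (W/√H) / √(W/H) = √W, whatever the waist and height.

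For C = 0.85, W = 60, H = 1.65:
- A = 0.85 / (0.109 × 60/√1.65) = 0.167
- B = 0.85 / (0.109 × √(60/1.65)) = 1.293
- Ratio = √60 = 7.7

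| Weight (kg) | 40 | 50 | 60 | 70 | 90 |
|---|---|---|---|---|---|
| B/A | 6.3 | 7.1 | 7.7 | 8.4 | 9.5 |

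**3. Sign of the change.** At fixed height, A follows C/W and B follows C/√W. If weight changes by a proportion g, the signs differ only when the proportional waist change lies between √(1+g) − 1 and g, that is, between about half of g and all of g.
- g = +5%: waist change between +2.5% and +5% (2.1 to 4.25 cm on 85 cm). A falls and B rises.
- g = −5%: waist change between −2.5% and −5%. A rises and B falls.
- Example, weight +3% and waist +2%: A changes by 1.02/1.03 − 1 = −1.0%; B by 1.02/√1.03 − 1 = +0.5%.

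Outside that window, or when waist and weight move in opposite directions, both forms give the same sign.

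**The case against.** **The formula conflict may not be in the protocol.** The two printings differ only in whether the exponent falls before or after a closing bracket. Other formulas in the text show similar damage. The arm-muscle formula in Sections 3.2.2 and 4.2.1 has no operator before 0.3142. The sample-size formula in Section 7.1 lacks a square on the sum of the z-values, yet the stated 112 needs it: (2.241 + 1.282)² × 4.5²/1.5² = 111.7. This objection stands in part. The source must be checked before the formula difference is pressed, but if the slip is in the protocol itself it still needs correcting. The waist conflict is in plain words and does not depend on any bracket.

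**A reader might infer that baseline follows Section 4.2.1 and follow-up follows Section 4.1.** The documents do not support that. The screening assessments are to be repeated at months 3 and 6, which favours the Section 4.2.1 formula at every visit. Nor is Section 4.1 about follow-up only: its numbered items include consent, demographics and allergy history. Some ambiguity remains, because item 11 speaks of measurement after enrolment and gives its own formula. Repeating Section 4.2.1 also does not settle the waist site, since that section names none.

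**A mix of formulas would be seen and could be repaired.** This is right. Values near 0.17 and 1.3 in one column would stand out, Section 10.2 requires the database to detect anomalies, and CI can be recomputed from waist, weight and height. No such repair exists for a waist taken at the wrong level.

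**These are secondary endpoints.** Also right. Section 7.7 makes no multiplicity adjustment for them, and they do not enter the success rule.

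**Conclusion.** The waist instructions contradict each other as written. On an assumed 85 cm waist and a 2 to 5 cm difference between sites, a change of site between visits would shift a patient's waist and CI by about 2% to 6%, with no means of correction later. The plan gives no data on the true difference between the two sites, so this is a range and not an estimate.

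The formula conflict is conditional on the source carrying both versions. If it does, CI values differ by a factor of 6.3 to 9.5 over 40 to 90 kg.

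Two stronger readings are tempting and should be resisted. The roughly eightfold gap comes from the formulas alone; the waist site adds only a few percent. A reversal in the direction of change is possible but not general: it needs waist and weight to move the same way, with the waist change inside the window shown above. The primary endpoints, the success rule and the sample size of 140 are untouched. The point deserves correction because the fix is almost free and the waist error is irreversible.

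**What to change.** 1. Name one waist landmark, in the same words, in Sections 3.2.2, 4.1 (item 11) and 4.2.1. Require it at every visit in every centre, and cover it in site training. This must be settled before measurement starts.
2. Check the CI formula in both sections against the source document, then print one form in both. The Section 4.2.1 form is the natural candidate, because the rule that screening assessments are repeated points to it.
3. Record waist, weight and height on the case report form and derive CI centrally, so that no centre calculates it by hand.

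The cost is a few text corrections and one derived variable in the database. No extra measurement or visit is needed.
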